4.10.1.4 Multiple Comparisons/Multiplicity

Not Applicable.

PAREXEL International
Statistical Analysis Plan Template for Early Phase Studies

Symphegen A/S

Sym013-01

4.10.1.5 Interim Analyses

No formal interim analysis is planned.

All relevant safety, PK and toxicity data will be reviewed on an ongoing basis throughout the trial, especially at various decision points for dose escalations and expansion.

4.10.1.6 Examination of Subgroups

Tumor Type will be used as a subgroup to summarize some study endpoints or as stratification factor in certain graphics as appropriately described in the text of this SAP. Tumor type categorization will be based on primary tumor site which may also be combined with tumor histology.

4.10.2 Analysis of Efficacy Variable(s)

All statistical analysis of the efficacy endpoints will be presented using the FAS.

4.10.2.1 Anti-Tumor Response according to RECIST v1.1

The following anti-tumor response endpoints will be measured in Part 1:

- Confirmed and unconfirmed BOR by RECIST v1.1 will be listed and summarized by dose regimen and dose level received using frequency distribution for the categories CR, PR, SD, PD, and Not Evaluable.
- Number and percentage of patients with documented confirmed and unconfirmed OR will be summarized by dose regimen and dose level using frequency distribution with the corresponding 95% exact Clopper-Pearson Confidence Intervals (CI) for binomial proportion. All documented ORs will be listed including duration (weeks) of response.
- Patients in DCR will be listed and summarized by dose regimen and dose level using frequency distribution with the corresponding 95% exact Clopper-Pearson Confidence Intervals (CI) for binomial proportion.
- Time to Progression (TTP)

PAREXEL International
Statistical Analysis Plan Template for Early Phase Studies

Symphogen A/S
Sym013-01

The median TTP, as well as 26 weeks and 52 weeks TTP rates and the corresponding 95% CIs will be estimated using the product-limit method and presented using a Kaplan-Meier plot. Number and percent of censored patients will be presented, also number and percent of patients censored for death will be presented.

- Changes in sum of diameters of target lesions from baseline to end of trial participation
Changes in the sum of diameters of target lesions from baseline to end of trial participation will be listed as percentage and absolute value, the best change (i.e., largest reduction or smallest increase) will be identified and presented using summary table and plotted with a waterfall plot. Change in sum of diameters will also be presented by primary tumor type.
- Results of the tumor evaluation by CT/MRI for target lesions, non-target lesions and timepoint tumor response will be listed, as well as derived target and non-target time point responses.

4.10.2.2 Tumor Markers

The date of the tumor evaluation and all test results will be listed.

4.10.3 Pharmacodynamic, Biomarkers and Immunogenicity

4.10.3.1 Pharmacodynamic, Biomarkers, Immunogenicity (ADA) and Archival Tumor

Exploratory analysis may be conducted according to the study exploratory objectives based on the available pharmacodynamic data.

Potential biomarkers of interest include genes, gene transcripts, and proteins of the HER family receptors and molecules of the mitogen-activated protein kinase (MAPK) and phosphoinositide 3-kinase (PI3K) pathways involved in HER signaling.

Results of pharmacodynamic biomarkers taken from blood samples will be listed. Blood sample results for anti-drug antibody will be listed. Cancer Gene Mutations will be listed as well.

Exploratory analysis of the biomarker profiles might be performed.

PAREXEL International
Statistical Analysis Plan Template for Early Phase Studies

Sympogen A/S

Sym013-01

4.10.3.2 Skin Biopsy

The location of the skin biopsy, the date taken, and expression results of EGFR and HER3 and proliferation marker Ki67 will be listed.

EGFR and HER3 receptor down modulation and changes in Ki67 in skin biopsies, measured by percentage and nominal change in target expression from baseline to end of Cycle 2 or PD (whichever comes first) in skin samples will be presented by tumor type using descriptive statistics.

After protocol amendment 6, (version 7.0), EGFR and HER3 receptor down modulation in skin biopsies, measured by percentage and nominal change in target expression from baseline to Cycle 1 day 8 and Cycle 1 day 15 in skin samples will be presented by trial part and tumor type using descriptive statistics, scatter plots of values at Cycle 1 day 8 and Cycle 1 day 15 versus baseline may also be produced.

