3 INVESTIGATIONAL PLAN

3.1 Overall Study Design and Plan

This is an open-label, multicenter trial composed of 2 parts in which Pan-HER will be evaluated when administered by the IV route to patients with advanced epithelial malignancies without available therapeutic options:

- Part 1 is a Phase 1a dose-escalation evaluating Q1W and Q2W schedules of administration in separate dose-escalation cohorts to determine the RP2D and regimen of Pan-HER.

PAREXEL International
Statistical Analysis Plan Template for Early Phase Studies

Symphogen A/S
Sym013-01

- During Part 1, cohorts of patients will receive increasing doses of Pan-HER on either Q1W or a Q2W schedule until establishment of the following for each schedule:
 - A maximum administered dose (MAD), the highest dose level administered (in mg/kg).
 - A maximum tolerated dose (MTD), the highest dose of SYM013 with <33% patients who have experienced dose limiting toxicity (DLT) as defined by the protocol during cycle 1 of study treatment. Q1W and Q2W regimens may have different MTDs;
 - A RP2D, determined based safety of Q1W and Q2W dose regimens as well as available PK and target engagement results, was to be identified. The RP2D may be equal to or lower than the MTD for the Q1W and/or Q2W dosing regimens.

The Part 1 starting dose of Pan-HER will be 1.0 mg/kg Q1W. The following dose levels of Pan-HER are planned to be evaluated:

Q1W

- Dose Level 1: 1 mg/kg Q1W
- Dose Level 2: 2 mg/kg Q1W
- Dose Level 3: 4 mg/kg Q1W
- *Dose Level 4P: 6 mg/kg Q1W + P (lower doses with prophylaxis may be explored, if indicated)
- *Dose Level 5P: 9 mg/kg Q1W + P
- *Dose Level 6P: 12 mg/kg Q1W + P (no patient enrolled in this dose level)
- *Dose Level 7P: 15 mg/kg Q1W + P (no patient enrolled in this dose level)
- *Dose Level 8P: 18 mg/kg Q1W + P (highest potential dose allowed per protocol) (no patient enrolled in this dose level)

PAREXEL International
Statistical Analysis Plan Template for Early Phase Studies

Symphogen A/S

Sym013-01

Q2W

- Dose Level 4: 6 mg/kg Q2W
- Dose Level 5: 9 mg/kg Q2W
- *Dose Level 5P: 9 mg/kg Q2W+ P
- *Dose Level 6P: 12 mg/kg Q2W+ P
- *Dose Level 7P: 15 mg/kg Q2W + P
- *Dose Level 8P: 18 mg/kg Q2W + P (highest potential dose allowed per protocol) (no patient enrolled in this dose level)

*Mandatory intensive IRR and oropharyngeal mucositis prophylaxis; 4-hour infusion (designated “P”)

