4.2 General Presentation Considerations

Baseline

‘Baseline’ is defined as the last available pre-treatment assessment, considering both scheduled and unscheduled assessments.

Safety assessments at Cycle 1 Day 1 with no time of assessment (i.e. Vital Signs and Body Measurements, ECOG PS, Physical Examination) are assumed to be taken pre-treatment.

End of Treatment (EOT)

‘End of Treatment’ is defined as the first assessment on or after the last dose of study treatment, considering both scheduled and unscheduled assessments.

Unscheduled assessments

Unscheduled assessments will be presented in listings in chronological order.

Post Baseline unscheduled assessments (for Clinical Laboratory, ECG QTc, etc.) will be used for determination of worst result (i.e. Maximum and Minimum post Baseline result) as well as the maximal laboratory CTCAE grade if applicable; also, all post baseline tumor evaluation assessments will be used to derive BOR.

Except considered as Baseline, EOT or worst result, unscheduled assessments will not be included in summaries.

PAREXEL International
Statistical Analysis Plan Template for Early Phase Studies

Symphogen A/S
Sym013-01

Treatment Day

‘Treatment Day’ will be calculated relative to the date of C1/D1 as follow:

- assessments taken before the first infusion of IMP

Treatment Day = Assessment Date - First IMP infusion Date

- assessments after the first infusion of IMP

Treatment Day = Assessment Date - First IMP infusion Date + 1.

Missing Data

In case of partially missing date of birth or date of diagnosis, the following rule will be applied: if year and months are known but day is missing, then the day will be imputed as 15th; in case of only year known, the day and month will be imputed as 15th June.

Specific rules for handling for missing efficacy assessments are detailed in section 4.10.1.3.

Methods for handling missing concomitant medication and adverse events dates are detailed in sections 4.8 and 3.2.4.2 respectively.

Imputations will be used to derive parameters, in listings original data will be presented as collected.

Data Listing

All original and derived parameters for all consented patients will be listed.

All listings will include scheduled and unscheduled measurements.

Unless specified otherwise, data in listings will be presented by dose regimen (Q1W or Q2W), dose group, patient, and visit (ordered by date and time within patient).

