All listings will display the same number of decimals as in the source data. All raw data will be reported exactly as provided.

Quantitative derived variables (e.g. Duration of Response, Time to Progression, Actual Treatment duration) will be shown with 1 decimal place (d.p.) precision.

PAREXEL International
Statistical Analysis Plan Template for Early Phase Studies

Symphegen A/S
Sym013-01

The data for the patients who consented but for any reason did not receive any dose of study drug (including screening failures) will be also listed but with a label of '*' and a footnote to flag these.

Efficacy, Exposure and PK/PD Data Listing will be based on Full Analysis Set.

Tables and Descriptive Statistics

Unless specified otherwise all tables and statistics will be presented using the FAS.

Evaluation of DLT will not be based on FAS but on DLT Analysis Set.

Unless specified otherwise summary tables and figures will be presented by dose regimen (Q1W or Q2W), dose group, and visit (where applicable); also, overall summaries will be shown for the two-dosage regimen and for all patients pooled together. In general, summary tables will be structured in three parts: first part will summarize overall results obtained in the two dose regimens Q1W, Q2W and in all patients pooled together; second part will display all dose groups within the dosage regimen Q1W; third part will display all dose groups within the dosage regimen Q2W.

In general, for variables showing multiple possible categories, these will be displayed with following the within variable logic criteria, for example: ECOG categories will be displayed from 0 and going to grow; where such a logic criterium does not exist (example: gender, ethnicity, SOC, PT), categories will be displayed by descending frequencies based on the overall all patients pooled together. In the end, the order used to show categories within variables should be the same in the three parts of each table.

Unless otherwise stated, continuous data will be summarized using descriptive statistics including: number of non-missing observations (n), arithmetic mean, standard deviation (SD), median, minimum, and maximum.

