Categorical data will be summarized in terms of the number of patients providing data at the relevant time point (n), frequency counts and percentages. Any planned collapsing of categories will be detailed in the SAP text and the data displays. Percentages will be calculated using n as the denominator. Changes from baseline in categorical data will be summarized using shift tables where appropriate.

PAREXEL International
Statistical Analysis Plan Template for Early Phase Studies

Symphogen A/S
Sym013-01

The following rules will apply to all descriptive statistic displays, except the PK concentrations and parameters that are reported in significant digits described in section 4.10.4.4 below, where d denotes the decimal places in the original reported value:

- n : 0 decimal places (d.p.)
- Mean: $d + 1$ d.p.
- Confidence Interval: $d + 1$ d.p.
- SD: $d + 2$ d.p.
- Median: $d + 1$ d.p..
- Minimum: d .
- Maximum: d .
- Statistics in percentage: 1 d.p.
- p-value: 4 d.p.
- Except for p-value, a maximum of 3 decimal places will be displayed.

P-values greater than or equal to 0.001, in general, will be presented to three decimal places. P-values less than 0.001 will be presented as “<0.001”.

Details for reporting of statistical summaries specific to PK are detailed in section 4.10.1.4.

Figures

If not otherwise specified, each figure will be presented separately for the two dose regimens (Q1W and Q2W) with differentiate legend to discriminate the dose groups within the regimen; moreover, an overall figure will also be presented with differentiate legend to discriminate the two dose regimens. In the end, there will be three panel for each figure: first panel will show all patients, second panel patients in Q1W regimen, third panel patients in Q2W regimen.

All figures will be produced in black and white.

PAREXEL International
Statistical Analysis Plan Template for Early Phase Studies

Symphogen A/S
Sym013-01

Specification for PK figures will be detailed in section 4.10.4.1.

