4.10.3.3 Tumor Biopsy

The date of the tumor biopsy, the tumor site, expression results of EGFR, HER2, and HER3 and Ki67 staining will be listed. EGFR, HER2 and HER3 receptor down modulation and changes in Ki67 in tumor biopsies (may not be available in Part 1), measured by percentage and nominal difference in target expression from baseline to end of Cycle 2 or PD (whichever comes first) in tumor biopsy samples will be presented by tumor type using descriptive statistics including scatter plots of values at end of Cycle 2 versus baseline.

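### The SAP groups skin and tumour target-engagement summaries by tumour type and names neither dose nor schedule, so the stated tables would pool doses for an endpoint that informs the RP2D.

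*SAP*

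**What the plan says.** SAP 4.10.3.2 covers skin in two statements. For sampling at the end of Cycle 2 or at progression, EGFR, HER3 and Ki67 change "in skin samples will be presented by tumor type using descriptive statistics". For sampling after Amendment 6 (Cycle 1 Day 8 and Day 15), EGFR and HER3 change "in skin samples will be presented by trial part and tumor type using descriptive statistics". SAP 4.10.3.3 covers EGFR, HER2, HER3 and Ki67 in tumour tissue, where change "in tumor biopsy samples will be presented by tumor type using descriptive statistics". None of these sentences mentions dose or schedule.

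The general rule is in SAP 4.2: "Unless specified otherwise summary tables and figures will be presented by dose regimen (Q1W or Q2W), dose group, and visit (where applicable"). That rule also gives pooled summaries for Q1W, for Q2W and for all patients. Unless otherwise specified, figures have a panel per regimen "with differentiate legend to discriminate the dose groups within the regimen". For listings the rule is that "data in listings will be presented by dose regimen (Q1W or Q2W), dose group, patient, and visit".

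The SAP keeps both the RP2D and target engagement as secondary objectives (2.1.2). In 3.1 it describes an RP2D that, on the basis of safety "as well as available PK and target engagement results, was to be identified".

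**The concern.** Part 1 is a dose escalation over two schedules. What a reader needs from the biopsy data is whether receptor down-modulation changes with dose and schedule. A row for one tumour type averages over whichever doses its patients received, and Part 1 admits any advanced epithelial malignancy (Protocol 6.1). If the two biopsy sections displace the 4.2 layout, the summary tables for a retained secondary objective do not display the factor that the trial varied. Any difference between rows could then reflect which tumour types entered which cohort. Target engagement would also be the only one of the three RP2D inputs whose stated summaries are not by dose.

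**Working it through.** No arithmetic decides this point. The check sets the relevant sections side by side.

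1. **Does the 4.2 default apply?** It holds unless something else is specified. 4.10.3.2 and 4.10.3.3 each name a grouping, and it is not dose. On plain reading that is a different specification.

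2. **How does the SAP mark tumour type as an extra cut?** In 4.10.2.1 the change in sum of diameters is *also* shown by primary tumour type, and section 6 gives that cut its own output (Table 14.2.4.4, beside Table 14.2.4.3). The biopsy sections have no such word, and section 6 lists one table each for skin (14.2.3.1) and tumour (14.2.3.2).

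3. **What happened to other summaries with the same protocol grouping?** Protocol 10.4.3 set safety summaries by trial part and tumour type.
   - Vital signs are now by regimen and dose group (SAP 4.11.7).
   - Physical examination is now by regimen and cohort (4.11.8).
   - Laboratory descriptive statistics are by regimen and dose group, with tumour type left for the box plots (4.11.4).
   - The biopsy sections received no such change.

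4. **Where does the grouping come from?** Protocol 10.4.5 prescribes trial part and tumour type for biopsy change. Protocol 10.4 defines a cohort as the dose cohort in Part 1 and the tumour type in Part 2. SAP section 1 says that nobody enrolled in Part 2 and that its analyses are omitted. The post-Amendment 6 skin sentence still groups by trial part, which now has one level. The wording looks like a Part 2 remnant; this is an inference.

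5. **How are the other RP2D inputs shown?** PK concentrations and parameters are tabulated by schedule and dose group (4.10.4.1, 4.10.4.3). DLTs are shown by regimen and dose (4.11.1).

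6. **What would still show dose?** Listings 16.2.6.4 and 16.2.6.5 do so under the listing rule. The skin scatter plots (Figures 14.2.1 to 14.2.3) should carry the dose-group legend by default. There are two gaps:
   - Those skin figures cover Cycle 1 Day 8 and Day 15 only. SAP 3.2.2 dates that sampling from Amendment 6; before then skin was sampled at the end of Cycle 2 or at progression. Section 6 lists no figure for the earlier sampling, so Table 14.2.3.1 is its only planned summary beyond a listing. Patients entered as of Amendment 6 number 1 + 1 + 4 + 3 + 7 + 3 = 19, in six dose-schedule groups from 1 to 9 mg/kg (Protocol 3.2.4.1). The documents do not say how many have paired skin samples.
   - In 4.10.3.3 the phrase "in tumor biopsy samples will be presented by tumor type using descriptive statistics including scatter plots" attaches the plots to the tumour-type grouping. The legend default for Figures 14.2.4 to 14.2.7 could therefore be read as displaced too.

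**The case against.** The strongest reply is that tumour type is a subgroup within the default layout and does not replace it. SAP 4.10.1.6 calls it a subgroup or a stratification factor. The titles of Tables 14.2.3.1 and 14.2.3.2 and of Figures 14.2.1 to 14.2.7 do not mention tumour type, whereas Table 14.2.4.4 and Figures 14.2.24 to 14.2.26 and 14.2.28 do. The laboratory box plots give a precedent: 4.11.4 describes them by visit and tumour type, yet section 6 also lists a set by visit alone. This makes the text ambiguous, so the loss of dose is not certain. It does not settle the matter in favour of dose, because a programmer would still face two conflicting instructions.

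Other points stand:
- The SAP follows its protocol here.
- The safety monitoring committee selects the RP2D from data available during the trial (Protocol 5.1, SAP 3.1), not from the final tables.
- All analyses are descriptive (SAP 4.10.1.2).
- With two dose groups of one patient each as of Amendment 6, patient-level plots and listings tell more than a mean and SD.
- Grouping by dose would not remove confounding between tumour type and cohort in a non-randomised escalation.

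A reader might infer that the planned outputs cannot show a dose relation, or that the RP2D objective cannot be answered. The documents do not support that, given the listings, the default legends and the committee's role.

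A reader might also count the levels that SAP 3.1 does not mark as empty and conclude that every tumour-type row pools ten groups over a 15-fold dose range. That is unsupported. The PK panels in 4.10.4.1 show eight groups up to 12 mg/kg, skin data are split over two sampling schedules, and nothing shows that any one row contains every group.

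**Conclusion.** The point holds in a limited form. On the plain reading, two summary tables, both flagged for the abbreviated report, would pool doses and schedules for an endpoint that informs the RP2D. The gap is widest for skin change to the end of Cycle 2, which has no figure. Individual values by dose group remain available in the listings and, by default, in the figures.

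The conclusion rests on two assumptions: that an explicit grouping counts as a different specification under 4.2, and that tumour-type rows contain more than one dose group. The second is likely given the entry criteria, but the documents give no tumour-type counts by cohort, so the extent of pooling cannot be stated.

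**What to change.** In SAP 4.10.3.2 and 4.10.3.3:
- State that Tables 14.2.3.1 and 14.2.3.2 present absolute and percentage change by dose regimen and dose group, with pooled summaries for Q1W, Q2W and all patients as in 4.2.
- Confirm that Figures 14.2.1 to 14.2.7 use the 4.2 panels with a dose-group legend.
- Keep tumour type only as an additional cut for tumour biopsies, and delete the reference to trial part.
- Record the departure from Protocol 10.4.5 in SAP 4.14.

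This needs no new data; only the grouping variable and a few lines of text change. The small downside is sparse cells, since some dose groups have one patient. In those cells the table would show the single value without an SD.

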4.10.3.3 Tumor Biopsy

The date of the tumor biopsy, the tumor site, expression results of EGFR, HER2, and HER3 and Ki67 staining will be listed. EGFR, HER2 and HER3 receptor down modulation and changes in Ki67 in tumor biopsies (may not be available in Part 1), measured by percentage and nominal difference in target expression from baseline to end of Cycle 2 or PD (whichever comes first) in tumor biopsy samples will be presented by tumor type using descriptive statistics including scatter plots of values at end of Cycle 2 versus baseline.

